#### **12.4. ECG**

A 12-lead, resting ECG will be obtained at the visits indicated in the SoA in Protocol Section 10.

Actual values and changes from baseline in ECG parameters (heart rate [bpm], PR Interval [msec], QRS Interval [msec], RR Interval [msec], QT Interval [msec], and QTc [msec]) will be summarized by visit using descriptive statistics. An outlier analysis will be performed that will summarize by treatment the frequency and percentage of participants who meet any of the following outlier criteria at each visit:

- QTc interval > 450 msec
- QTc interval > 480 msec
- QTc interval > 500 msec
- QTc interval increases from baseline > 30 msec
- QTc interval increases from baseline > 60 msec

This outlier analysis will be repeated summarizing frequency and percentage of participants by treatment who meet any of these outlier criteria at any time during the trial.

All ECG parameters, including overall ECG evaluation will be provided in data listings.

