10. STUDY PROCEDURES

Table 4 outlines the timing of procedures and assessments to be performed throughout the study. Section 12.5 specifies laboratory assessment samples to be obtained. See Sections 11 and 12 for additional details regarding efficacy assessments and safety assessments, respectively.

 Table 4.
 Schedule of Assessments

	Screening		Follow up						
Procedure	Between Day -28 and -1	Day 1 (Baseline)	W1 (±1d)	W2 (±1d)	W4 (±2d)	W8 (±3d)	W12 (±3d)	W16 (EOT/ET; ±3d)	W20 (±3d)
Informed consent (before any study procedures)	X								
Demography	X								
Medical history, including medication, alcohol, and smoking history (last 6 months)	X								
Concurrent medication review	X	X	X	X	X	X	X	X	X
Inclusion and exclusion criteria	X	X							
Physical examination ^a	X	X						X	X
12-lead ECG (single measurement)	X				X	X		X	
Vital signs ^b	X	X			X	X	X	X	X
Weight ^c	X	X			X	X	X	X	X
Height ^c		X							
BMI ^c		X				X		X	X
Waist and hip circumferences ^c		X				X		X	X
Randomization		X							
Adverse events	X	X	X	X	X	X	X	X	X
Blood sample for serology (HIV antibody, HBV, HCV, HBsAg, HBcAb, and HBsAb)	X								
Safety laboratory assessments (hematology, serum chemistry, urinalysis)	X	X			X	X		X	
Cardiovascular risk factor laboratory assessments ^{c,d}		X						X	
Pregnancy test ^c	X	X			X	X	X	X	
Blood samples for drug and metabolite PK analysis: trough levels (before study drug administration)		X			X	X		X	
Blood samples for drug PK profile (optional)					X			X	
		X						X	

	Screening		Follow up						
Procedure	Between Day -28 and -1	Day 1 (Baseline)	W1 (±1d)	W2 (±1d)	W4 (±2d)	W8 (±3d)	W12 (±3d)	W16 (EOT/ET; ±3d)	W20 (±3d)
IGA, BSA, and PASI	X	X			X	X	X	X	X
PGA-F		X						X	X
Scalp Psoriasis ss-IGA		X						X	X
Scalp itch NRS		X						X	
		X						X	X
PSS		X			X	X	X	X	X
C-SSRS	X	X			X	X	X	X	X
DLQI		X						X	X
HADS		X			X	X	X	X	X
Dispense study drug		X	Xh	Xh	X	X	X		
Collect study drug including packaging			Xh	Xh	X	X	X	X	
Compliance check			X	X	X	X	X	X	

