#### 4.2.2. Exclusion Criteria

Patients are excluded from the study if any of the following criteria apply:

1. Therapy-resistant psoriasis defined as  $\geq 2$  treatment failures due to inadequate efficacy within the past 5 years of any biologic therapies (including but not limited to etanercept, adalimumab, infliximab, certolizumab pegol, guselkumab, secukinumab, risankizumab, ixekizumab, tildrakizumab, or ustekinumab) administered in adequate dose and duration according to the label or local/national guidelines (patients who stopped systemic treatment for reasons not related to lack of efficacy are not excluded).
2. Unstable psoriasis or PsA with acute deterioration within 4 weeks of the Screening visit.
3. History of allergy or hypersensitivity to any component of the study treatment.
4. Active infection (eg, bacteria, viral, fungal) requiring treatment with systemic antibiotics within 4 weeks of the Screening visit.
5. Malignancy or history of malignancy except for treated (ie, cured) basal cell skin carcinomas.
6. Current diagnosis of predominant guttate, erythrodermic, exfoliative, or pustular psoriasis, or of drug-induced psoriasis, or other skin conditions that might confound the evaluation of psoriasis vulgaris, as judged by the Investigator (eg, atopic dermatitis, lupus).
7. Any recurrent medical condition associated with serious GI diseases, such as inflammatory bowel disease.
8. Any medical or psychiatric condition (eg, current major depression with a score for depressive symptoms  $\geq 15$  of HADS at Baseline, schizophrenia, suicidal behavior, psychiatric hospitalization within the prior year) which, in the Investigator's opinion, would preclude the patient from adhering to the protocol, completing the study per protocol, and/or would place the patient at unacceptable risk for receiving the investigational therapy.
9. Any therapies and systemic treatments as described in Protocol Section 9.5.2 which do not comply with the indicated washout interval. [REDACTED].
10. Any previous treatment with orismilast or failure of treatment with apremilast or any other systemic PDE4 inhibitor as described in Protocol Section 9.5.2.
11. Any condition, including laboratory or ECG abnormalities, that places the patient at an unacceptable risk to participate in the study or confounds the ability to interpret data from the study.
12. Severe hepatic impairment based upon medical history and laboratory abnormalities (eg, low albumin and abnormal bilirubin).

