14.3.4.1		Clinical Laboratory Data	
14.3.4.1.1	14.3.4.1.1	Chemistry: Summary by Visit and Change from Baseline	Safety Population
	14.3.4.1.2	Chemistry: Maximum Shift From Baseline to Week 16 Relative to the Normal Range	Safety Population
	14.3.4.1.3	Listing of Chemistry Abnormal Results	Safety Population
	14.3.4.2.1	Hematology: Summary by Visit and Change from Baseline	Safety Population
	14.3.4.2.2	Hematology: Maximum Shift From Baseline to Week 16 Relative to the Normal Range	Safety Population
	14.3.4.2.3	Listing of Hematology Abnormal Results	Safety Population
	14.3.4.3.1	Urinalysis: Summary by Visit	Safety Population
	14.3.4.3.2	Urinalysis: Maximum Shift From Baseline to Week 16 Relative to the Normal Range	Safety Population
	14.3.4.3.3	Listing of Urinalysis Abnormal Results	Safety Population
		Vital Signs	
	14.3.4.4.1	Vital Signs: Summary by Visit and Change from Baseline	Safety Population
		ECG	

This document is confidential.

Header	Table Number	Name	Analysis Population
	14.3.4.4.2.1	ECG Parameters: Summary by Visit and Change from Baseline	Safety Population
	14.3.4.4.2.2	ECG Outlier Analysis by Visit	Safety Population
	14.3.4.4.2.3	ECG Outlier Analysis at Any Time Post-baseline	Safety Population
		Physical Examination	
	14.3.4.4.3	Shift in Physical Examination between Baseline and each Visit	Safety Population
		Other Safety	
	14.3.4.4.4.1	Hospital Anxiety and Depression Scale (HADS): Summary by Visit and Change from Baseline	Safety Population
	14.3.4.4.4.2	Hospital Anxiety and Depression Scale (HADS): Summary by Category and Visit	Safety Population
	14.3.4.4.4.3	Hospital Anxiety and Depression Scale (HADS): Shift from Baseline	Safety Population
	14.3.4.4.5	Number of Patients with Suicidal Ideation, Suicidal Behavior, and Self-injurious Behavior without Suicidal Intent Based on the C-SSRS	Safety Population
	14.3.4.4.6	Shift in C-SSRS between Baseline and each Visit	Safety Population

This document is confidential.

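### The any-time QTc outlier table is worded in two ways, and its absolute rows cannot separate newly crossed thresholds from prolongation that was present at Screening and persists

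*SAP*

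**What the plan says.** SAP 12.4 lists five QTc outlier criteria. Three are absolute: "QTc interval > 450 msec", and the same at 480 and 500 msec. Two are relative to baseline: "QTc interval increases from baseline > 30 msec", and the same at 60 msec. They are tabulated once by visit ("ECG Outlier Analysis by Visit", Table 14.3.4.4.2.2) and once more as the "frequency and percentage of participants by treatment who meet any of these outlier criteria at any time during the trial". The index of tables in SAP section 18 titles this second output "ECG Outlier Analysis at Any Time Post-baseline" (Table 14.3.4.4.2.3).

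Other provisions bear on the point:

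- Protocol Table 4 schedules a single 12-lead ECG at Screening and at Weeks 4, 8 and 16, and none on Day 1.
- SAP 7.2 takes the last non-missing pre-dose value as baseline. For QTc this is normally the Screening ECG.
- Eligibility has no numerical QTc limit. Exclusion criterion 11 covers "Any condition, including laboratory or ECG abnormalities, that places the patient at an unacceptable risk to participate in the study". Protocol 12.4 has the Investigator check the Screening trace for excluding cardiac disease, and requires a repeat ECG after a clinically significant abnormality or an artifact.
- SAP 7.1 keeps unscheduled data out of by-visit summaries, but uses them for the worst case in safety shift tables and to avoid missing data. SAP 7.4 keeps unscheduled assessments out of summaries except to fill a missing Week 4 to 20 value, and lets a pre-dose one serve as baseline.
- SAP section 12 plans no inferential analysis of safety.

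**The concern.** The text and the table title give different time spans for one output. The table shells are a separate document (SAP section 21), so from the SAP alone a programmer would have to choose.

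Settling the time span would not settle the reading of the absolute rows. A patient above a threshold before dosing and again on treatment is counted in the same way as a patient who crossed it on treatment. The ECG endpoint in SAP 5.5 is change from baseline, and elsewhere the SAP compares with baseline. In the laboratory tables of SAP 12.2, a patient high at baseline who does not become low is classed as no change. Physical examination, HADS and C-SSRS each have a shift table. ECG has none, so no planned table shows who newly crossed 450, 480 or 500 msec.

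At stake is how easily a descriptive QT table by dose can be read, in a trial whose secondary objective is to identify the dose with the best benefit/risk ratio. No QT signal is implied. The protocol reports some hERG inhibition in vitro (5.2.1), but no QT effect in minipigs and no clinically relevant ECG findings in volunteers given the modified-release tablet (5.4.1).

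**Working it through.** The documents state no number of QTc outliers, so there is no figure to reproduce. The check sets the provisions side by side and then sizes the issue on stated assumptions.

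**1. Which patterns are counted.** Take Screening as baseline and look at the row for QTc above 450 msec (values in msec).

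| Pattern | Screening | Highest post-baseline | Text of 12.4 | Table title | Increase >30 row | At or below 450 at baseline, above it afterwards |
|---|---|---|---|---|---|---|
| A | 460 | 450 or less | counted | not counted | no | no |
| B | 460 | 460 | counted | counted | no (460 − 460 = 0) | no |
| C | 450 | 460 | counted | counted | no (460 − 450 = 10) | yes |
| D | 455 | 478 | counted | counted | no (478 − 455 = 23) | no |

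- A is the only pattern on which the text and the title disagree.
- B and C look the same in all five planned outlier rows: both are above 450, and neither meets any other criterion. The same holds for any baseline from 430 to 450 with a post-baseline maximum of 460, because 460 − 430 = 30 is not above 30. The increase rows therefore do not replace a new-crossing row.
- D shows the cost of replacing the absolute rows with conditioned ones. D is above 450 already, is not above 480, and rises by less than 30, so D would leave every outlier row.

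**2. Unscheduled ECGs.** The any-time table is neither a by-visit summary nor a shift table, so neither rule in SAP 7.1 clearly covers it. Under SAP 7.4 a repeat ECG stays out of summaries when the scheduled value exists. A repeat above 500 msec after a scheduled value below it could go uncounted. Yet an unscheduled ECG before dosing can set the baseline.

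**3. Size under an assumed prevalence.** Input from SAP 4.3: about 50 patients per arm. Assumption, not in the documents: 3-10% above 450 msec at Screening.

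- Above 450 at Screening, per arm: 50 × 0.03 = 1.5 to 50 × 0.10 = 5.
- If only half are above 450 again after baseline: 1.5 × 0.5 = 0.75 to 5 × 0.5 = 2.5. Under the table title, 1.5-5 is thus an upper bound, reached only if every case persists.
- Chance difference between two arms in these counts: SD = √(2 × 50 × p × (1 − p)). At p = 0.03 this is √2.91 = 1.7 patients; at p = 0.10 it is √9 = 3.0.
- An excess of 2 patients (50 × 0.04, where the 4% is also an assumption) is 2/1.7 = 1.2 down to 2/3.0 = 0.7 of that SD.

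**4. Illustrative simulation.** There is no drug effect, with one Screening and three post-baseline ECGs. All QTc inputs are assumed: mean 410, 420 or 430 msec, with between/within-patient SD 15/10 or 18/8 msec. The entries are expected patients per 50 above 450 msec.

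| Mean, SDs | At Screening | Any time incl. Screening | Any time post-baseline | Post-baseline, not at Screening |
|---|---|---|---|---|
| 410, 15/10 | 0.66 | 1.84 | 1.52 | 1.18 |
| 410, 18/8 | 1.05 | 2.31 | 2.00 | 1.26 |
| 420, 15/10 | 2.39 | 5.88 | 5.00 | 3.48 |
| 420, 18/8 | 3.18 | 6.20 | 5.51 | 3.02 |
| 430, 15/10 | 6.71 | 13.90 | 12.24 | 7.19 |
| 430, 18/8 | 7.78 | 13.34 | 12.17 | 5.57 |

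- Dropping Screening removes 0.3 (2.31 − 2.00) to 1.7 (13.90 − 12.24) patients per 50.
- Adding the baseline condition removes a further 0.3 (1.52 − 1.18) to 6.6 (12.17 − 5.57).
- The two 420 msec cases fall inside the assumed 3-10% (2.39/50 = 4.8%; 3.18/50 = 6.4%). Their persistent cases are 5.00 − 3.48 = 1.5 and 5.51 − 3.02 = 2.5 per arm, within the bound in step 3. The 6.6 comes from a case with 7.78/50 = 15.6% at Screening, outside that range.
- New crossings remain without any drug effect, so the new-crossing row also has to be read against placebo.

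**The case against.** A reader might infer that every patient with a prolonged QTc at Screening is counted as an on-study outlier. The documents do not support that. The table that carries out the sentence in SAP 12.4 is titled post-baseline, so prolongation seen only at Screening (pattern A) is not counted there. What stands against the plan on this point is a mismatch of wording.

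A reader might also infer a biased comparison between doses. Allocation is randomised 1:1:1:1, so pre-existing prolongation is balanced in expectation and adds background to every arm. No test or decision rule uses these counts.

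The plan also has partial safeguards. The increase rows use baseline, QTc change is summarised by visit, a by-visit outlier table is planned, and all ECG parameters are listed. Exclusion criterion 11 and the Screening review may keep out some patients with abnormal traces. The unseen shells may already show a baseline row. All this limits the consequence. It does not identify who newly crossed a threshold, except by reconstruction from listings.

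Finally, nothing in the documents requires counts conditioned on baseline, and replacing the absolute rows would lose pattern D. That objection stands, and the new rows should be added beside the existing ones.

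**Conclusion.** The point holds as a minor one. SAP 12.4 and its table title disagree on whether the pre-dose ECG is in scope. On either wording, the absolute rows mix new crossings with prolongation that was present at Screening and persists. The handling of unscheduled ECGs in this table is also left open. The gain from a change is a descriptive safety table that is easier to read, not the removal of a systematic bias.

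The size cannot be derived from the documents. The 1.5-5 patients per arm is an upper bound on persistent cases above 450 msec. It rests on an assumed 3-10% Screening prevalence and on every case persisting. No figure is offered for 480 or 500 msec.

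**What to change.** In SAP 12.4, end the sentence on the repeated outlier analysis with *at any time post-baseline, including unscheduled ECGs*, so that it matches the title of Table 14.3.4.4.2.3 and settles the status of repeat ECGs.

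Keep the three absolute rows and the two increase rows. For each absolute threshold add:

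- a row for patients at or below it at baseline and above it post-baseline, with patients at or below it at baseline as denominator;
- a row with the number already above it at baseline.

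The cost is one changed sentence, a filter in one program and six more table rows (3 thresholds × 2). No new data are needed.

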#### **12.5. Physical Examination**

A complete physical examination will be performed at Screening and Week 16. A limited physical examination will be conducted at Day 1 and Week 20.

A shift table to demonstrate changes in physical examination from baseline to all post-baseline visits by treatment will be generated.

Physical examination data will be listed.

#### **12.6. The Hospital Anxiety and Depression Scale**

The HADS is a patient reported outcome (PRO), comprises 7 questions for anxiety and 7 questions for depression with each answer being graded from 0 to 3 with a higher score indicating a worse condition. For each group of questions, scores of less than 7 indicate noncases, whereas 8 to 10, 11 to 14, and 15 to 21, indicate mild, moderate, or severe anxiety or depression, respectively. HADS will be collected at different time points as per the SoA in Protocol Section 10.

Actual values and changes from baseline in HADS scores (depression, anxiety and total) will be summarized by treatment. A summary table presenting the frequency and percentage of participants by treatment within categories (< 7, 8 – 10, 11 – 14 and 15 – 20) for anxiety and depression at each visit will be generated. A shift table to demonstrate changes in anxiety total score and depression total score from baseline to all post-baseline visits by treatment will be generated.

HADS scores, questions and answers will be provided in data listings.

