12.7. The Hospital Anxiety and Depression Scale

The HADS is a PRO and comprises of 7 questions for anxiety and 7 questions for depression with each answer being graded from 0 to 3 with a higher score indicating a worse condition. For each group of questions, scores of less than 7 indicate noncases, whereas 8 to 10, 11 to 14, and 15 to 21, indicate mild, moderate, or severe anxiety or depression, respectively. The HADS is one of the National Institute for Health and Care Excellence recommended tools for diagnosis of depression and anxiety.

Any patient with a score for depressive symptoms ≥15 at Baseline will not be eligible for randomization in the study. Patients with a clinically significant worsening of depressive symptoms or new occurrence of clinically significant depression during the study may be referred to a mental health specialist (psychiatrist or clinical psychologist) for further evaluation.

After a mental health specialist evaluation, the final decision on restarting or permanently discontinuing study treatment will be at the discretion of the Investigator in consultation with the mental health specialist. These cases should be reported as an AESI. Refer to Section 0.

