12.9.2. Adverse Events of Special Interest

An AESI (serious or non-serious) is one of scientific and medical concern, for which ongoing monitoring and rapid communication by the Investigator to the sponsor could be appropriate. AESIs must be reported within 24 hours of occurrence or when the Investigator becomes aware of the event, following SAE reporting procedures (Section 12.9.4). Such an event might require

further investigation in order to characterize and understand it. Depending on the nature of the event, rapid communication by the trial sponsor to other parties (eg, regulators) might also be warranted.

In this trial, the following AEs are to be considered AESIs:

- Any AE of occurrence of suicidal ideation or behavior, including a positive response to question 1 to 5 of C-SSRS
- A depression assessed as moderate or worse by the Investigator or a score ≥15 in the HADS score
- Any grade 3 or higher psychiatric condition
- Any weight loss >5% compared to Baseline, and/or
- Any of the following GI TEAEs: vomiting, diarrhea with an increase of at least four stools per day over Baseline (Grade 2 CTCAE) for at least 3 days.

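### The HADS category table in SAP 12.6 has no row for subscale scores of 7 or 21, so its counts fall short whenever either score occurs and a 21 is not counted as severe.

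*SAP*

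**What the plan says.** SAP 12.6 describes the HADS as an instrument that "comprises 7 questions for anxiety and 7 questions for depression with each answer being graded from 0 to 3". Higher scores are worse. The section then sets severity bands for the two subscales. Noncases lie below 7, and the other bands are these: "8 to 10, 11 to 14, and 15 to 21, indicate mild, moderate, or severe anxiety or depression, respectively".

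The next paragraph specifies a table of numbers and percentages of patients "by treatment within categories (< 7, 8 – 10, 11 – 14 and 15 – 20) for anxiety and depression at each visit". The Index of Tables (SAP 18) lists it as Table 14.3.4.4.4.2, "Hospital Anxiety and Depression Scale (HADS): Summary by Category and Visit", in the Safety Population.

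Protocol 12.7 has the same severity wording as the SAP text: "scores of less than 7 indicate noncases, whereas 8 to 10, 11 to 14, and 15 to 21, indicate mild, moderate, or severe". The scoring key on the form in Protocol Appendix 9 differs: 0–7 is normal, 8–10 borderline and 11–21 abnormal.

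Neither SAP 12.6 nor the table index gives an extra row, a footnote or a rule for a score that falls between the bands.

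**The concern.** A category table should place every possible score in exactly one row. This one leaves out two.

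The top category stops at 20, although the preceding paragraph takes the severe band to 21. A patient at 20 would be counted as severe and a patient at 21 would not. The bottom category stops below 7 and the next starts at 8, so a 7 is unclassified, although the form treats it as normal.

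HADS is a named safety endpoint, and Protocol 5.3 says depression will be monitored as a potential effect of the drug class. Table 14.3.4.4.4.2 is the only planned output whose stated bands show anxiety and depression severity by arm and visit. If it is programmed as written, its rows can fall short of the number assessed, the lowest band is understated relative to the form's key, and the worst possible score is lost from the severe row. A programmer who notices the gap would have to choose a band without a written rule.

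**Working it through.** **Inputs**

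- Seven items per subscale, each scored 0 to 3 (SAP 12.6; the same in Protocol 12.7).
- Table categories: <7, 8–10, 11–14, 15–20 (SAP 12.6).
- Text bands: <7, 8–10, 11–14, 15–21 (SAP 12.6 and Protocol 12.7).
- Form key: 0–7, 8–10, 11–21 (Protocol Appendix 9).
- Planned size: about 200 patients, 50 per arm (SAP 4.3).

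**Step 1: range of the subscale.** The maximum is 7 × 3 = 21 and the minimum is 0, so there are 22 possible whole-number scores. This reproduces the upper limit of 21 in the SAP's own severe band.

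**Step 2: each set of bands against all 22 scores.**

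| Bands | Scores with no category | Scores in two categories |
|---|---|---|
| SAP table: <7, 8–10, 11–14, 15–20 | 7 and 21 | none |
| SAP and protocol text: <7, 8–10, 11–14, 15–21 | 7 | none |
| Appendix 9: 0–7, 8–10, 11–21 | none | none |
| 0–7, 8–10, 11–14, 15–21 | none | none |

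The table covers 7 + 3 + 4 + 6 = 20 of 22 scores. The gap at 21 occurs only in the SAP table. The gap at 7 is already present in the text of both documents.

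**Step 3: how often it could matter.** The documents give no HADS distribution, so this step is an assumption. I used a negative binomial distribution, chosen for its right skew, truncated to 0–21, with size r = mean² / (SD² − mean) and probability p = mean / SD². For example, mean 4 and SD 3.5 give r = 16 / (12.25 − 4) = 1.94 and p = 4 / 12.25 = 0.327. The mean and SD are the values before truncation.

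| Assumed mean / SD | P(score 7) | Of 50 | Of 200 | P(score 21) | Of 200 | P(<7) | P(0–7) |
|---|---|---|---|---|---|---|---|
| 2 / 2.5 | 2.0% | 1.0 | 3.9 | 0.008% | 0.02 | 93.9% | 95.9% |
| 3 / 3 | 3.5% | 1.8 | 7.1 | 0.020% | 0.04 | 88.2% | 91.8% |
| 4 / 3.5 | 5.2% | 2.6 | 10.3 | 0.053% | 0.11 | 80.5% | 85.7% |
| 5 / 3.8 | 6.8% | 3.4 | 13.6 | 0.090% | 0.18 | 71.9% | 78.7% |
| 6 / 4 | 8.3% | 4.2 | 16.7 | 0.138% | 0.28 | 62.1% | 70.5% |

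The understatement of the lowest band equals P(score 7), because P(0–7) − P(<7) = P(7).

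**Step 4: chance that an arm is affected.** The chance of at least one 7 among 50 patients on a given subscale at a given visit is 1 − (1 − P(7))^50. That is 63% for the first row and 99% for the last. The schedule in Protocol Table 4 has HADS at six visits (Day 1 and Weeks 4, 8, 12, 16 and 20). With two subscales and four arms, the table has 6 × 2 × 4 = 48 blocks of counts. It is very likely that some of them would not add up.

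**The case against.** No reading of the text closes the gaps. The case against concerns weight and wording, and most of it stands.

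- **It is one descriptive table.** SAP 12 plans no inference on safety. The summary of actual values and changes (Table 14.3.4.4.4.1) and the listings keep every patient. The rule for ineligibility on depressive symptoms and the one for events of special interest, "A depression assessed as moderate or worse by the Investigator or a score ≥15 in the HADS score", use 15 or more, which has no upper gap. A depression score of 21 therefore still triggers reporting. For an anxiety score this is less clear, because the rule does not name the subscale. All of this limits the consequence.
- **The shortfall is conditional.** The rows fail to add up only where a 7 or a 21 occurs. This is correct, and the heading says so.
- **The two gaps are unequal.** A 21 is very unlikely, and a depression score that high would already bar randomization at Baseline. The gap at 7 is the one that will affect counts. The gap at 21 is still a plain contradiction within one SAP section.
- **Calling the lowest band understated depends on Appendix 9.** Protocol 18 says its scales are samples and that the study versions may differ. From the body text alone, a 7 is unclassified rather than normal. Either way it has no row.
- **The shells were not available.** SAP 21 places them in a separate document, and they may already use better bands. That would not correct the SAP text.

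**Conclusion.** The concern holds. As written, 2 of the 22 possible subscale scores have no category in Table 14.3.4.4.4.2, and the SAP contradicts its own severe band. This follows from the documents alone.

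How many patients are affected is not known from the documents. Under the assumed distributions, 2.0% to 8.3% of patients per subscale and visit (about 4 to 17 of 200, or 1 to 4 of 50) would be missing because of a 7. Fewer than one in 200 would be missing because of a 21. These figures illustrate scale and are not estimates for this trial.

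No efficacy result, eligibility rule or event-reporting rule changes. The bands of the HADS shift table (Table 14.3.4.4.4.3) are not stated, so no error is claimed there. The text should be corrected before the table is produced.

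**What to change.** In SAP 12.6 and in the shell for Table 14.3.4.4.4.2, use 0–7, 8–10, 11–14 and 15–21. All of these limits already appear in the documents: the lower band comes from Appendix 9, and the split at 14/15 and the upper limit come from the SAP and protocol text, since Appendix 9 has a single 11–21 band. If the shift table is built on bands, use the same ones there.

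Also reconcile the lower cut-off in the text of SAP 12.6 and Protocol 12.7 with the key in Appendix 9, so that a score of 7 is classified the same way throughout.

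The cost is one line in the SAP and one table shell. Protocol 15 lets the SAP prevail where the two differ, so the table can be corrected without a protocol amendment. Aligning the wording of Protocol 12.7 would fit the administrative class in Protocol 16.6.1, which goes to the ethics committees for information only.
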